7.3.2 Analysis

No analyses will be performed

7.3.3 Presentation

The PASS score will be presented using summary statistics and presented in tables and graphs. The graphs will be the mean value at each visit including the 2-standard error of the mean.

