### **5.3 Prohibited Medications**

Any medication, with the exception of those listed below, may be given at the discretion of the PI. Immunosuppressive medications/immunotherapy that should not be administered during the study include:

- Chemotherapy
- Cyclosporine, Tacrolimus
- Sirolimus, Everolimus
- Azathioprine
- Cyclophosphamide
- Methotrexate
- Mycophenolate
- Leflunomide
- Biologics/Monoclonals: abatacept, adalimumab, alemtuzumab, anakinra, basilizimab, belimumab, bevacizumab, brodalumab, canakinumab, certolizumab, cetuximab, daclizumab, eculizumab, etanercept, golimumab, infliximab, interferon, ixekizumab, muromonab, natalizumab, omalizumab, rituximab, secukinumab, tocilizumab, trastuzumab, ustekinumab, vedolizumab

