4.8 Handling of Drop-outs, Missing Data and Outliers

Outliers will be included in summary tables and listings, and will not be handled separately in any analyses. No imputation of missing data will be performed (however, will data entered in unscheduled visit be placed to the nearest applicable visit with missing values).

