7.3 Secondary Endpoints - PASS score

7.3.1 Definition

The definition of the PASS score is in accordance with the description below:

Calculated every 12 hours from 1st vital signs taken in the Emergency Department

Organ Failure Score: # Organs x 100 for each system

Organ Failure Definition: Modified Marshall Scoring System (adapted from Banks et al⁴)

Organ system	Score				
	0	1	2	3	4
Respiratory (PaO ₂ /FiO ₂)	>400	301–400	201–300	101–200	≤101
Renal					
Serum creatinine, µmol/L	≤134	134–169	170–310	311–439	>439
Serum creatinine, mg/dL	<1.4	1.4–1.8	1.9–3.6	3.6–4.9	>4.9
Cardiovascular (systolic blood pressure, mmHg) ^b	>90	<90, fluid responsive	<90, not fluid responsive	<90, pH <7.3	<90, pH <7.2

^aA score of 2 or more in any system defines the presence of organ failure

^bOff inotropic support

- Mechanical ventilation counts as respiratory organ failure
- New onset dialysis included as renal failure

SIRS (Systemic Inflammatory Response Syndrome): # SIRS Criteria satisfied x 25 for each criteria. (See below)

- Heart Rate > 90 beats per minute
- Temperature > 38 Celsius or < 36 Celsius
- White blood cell count < 4000 or > 12000
- Respiration > 20/minute

Take the most extreme value within each 12 hour window

Take the WBC from the most recent prior CBC if none available in a given 12 hour window

Abdominal Pain Score: Abdominal pain (0-10) x 5

- Highest numerical value in each 12 hour window

Morphine Equivalent Dose Score: Morphine Equivalent Dose x 5

- For consistency will be using IV MED (typical MED is for oral)
- Common conversions: (easiest to convert to IV)
- Morphine IV to PO is 1 to 3 (ie morphine 10 mg IV = 30 mg PO)
- Dilaudid IV to PO is 1 to 4 (ie dilaudid 1.5 mg IV = 7.5 mg PO)
- Dilaudid IV to Morphine IV is 1:7
- Note: 1 po MED = 30 mg oral morphine
- (refer to tables for more specific conversion)

	Parenteral	Oral
Morphine	10	30
Buprenorphine	0.3	0.4 (sl)
Codeine	100	200
Fentanyl	0.1	NA
Hydrocodone	NA	30
Hydromorphone	1.5	7.5
Meperidine	100	300
Oxycodone	10	20
Oxymorphone	1	10
Tramadol	100	120

Equianalgesic dose conversions. For calculation of Pancreatitis Activity Score:

1 MED (morphine equivalent dose) = 1 mg parenteral morphine = 3 mg oral morphine.

Tolerating Solid Diet Score: (yes=0, no=1) x 40

- Retrospective analysis: based on change in diet order
- Prospective analysis: tolerating at least 50% of solid meal without increase abdominal pain or vomiting

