7.8.3 Presentation

All including item and total scores will be presented using summary statistics.

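### PASS is presented only as a total, although its opioid item is uncapped, can outweigh organ failure, and is summarised nowhere on its own

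*SAP*

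**What the plan says.** PASS is a listed secondary efficacy endpoint (SAP 3.1.4). SAP 7.3.1 gives it five items:

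- organ failure: "Organ Failure Score: # Organs x 100 for each system", over three organ systems;
- SIRS: 25 points for each of four criteria;
- abdominal pain: the 0 to 10 rating times 5;
- solid diet: 0 or 40;
- opioids: "Morphine Equivalent Dose Score: Morphine Equivalent Dose x 5", with no upper limit stated.

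The unit for the last item is set by a line labelled for the PASS calculation: "1 MED (morphine equivalent dose) = 1 mg parenteral morphine = 3 mg oral morphine". The same section also contains "Note: 1 po MED = 30 mg oral morphine".

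The derivation ends with the total and its change from baseline. SAP 7.3.3 then states "The PASS score will be presented using summary statistics and presented in tables and graphs", and the graph is the mean at each visit with 2 standard errors. For SOFA, by contrast, SAP 7.8.3 says "All including item and total scores will be presented using summary statistics", and SAP 7.2.3 likewise asks for each individual CT scale.

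Opioids otherwise appear only in the concomitant-medication listing and the ATC-code table (SAP 6.2). On extreme values, SAP 4.8 says: "Outliers will be included in summary tables and listings, and will not be handled separately in any analyses". The trial is open label, and Protocol 5.3 says: "Any medication, with the exception of those listed below, may be given at the discretion of the PI". Immunosuppressive drugs are the listed exceptions.

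**The concern.** The opioid item is the only one without a ceiling, and the only one that is directly a prescribing decision. Protocol 1.1 describes opioids as the usual initial analgesic, so the item will rarely be zero. The clinicians who set the dose know whether the patient is on CM4620-IE, and the guideline summary in Protocol Appendix 7 gives no analgesic regimen that would standardise it.

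If the mean PASS curves separate, a reader will take this as a difference in pancreatitis activity. The same separation could come from different opioid prescribing with organ failure, SIRS, pain and diet unchanged. With only the total shown, the planned summaries do not tell the two apart. PASS has no planned test, so its tables and graphs are the whole of its analysis.

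**Working it through.** **Group sizes.** The cohorts sum to the plan's stated total: 4 + 4 + 8 + 8 = 24. At 3:1, the first phase gives 8 × 3/4 = 6 lower-dose patients and 2 controls. The second gives 16 × 3/4 = 12 higher-dose patients and 4 controls. The groups are therefore 6 control, 6 lower dose and 12 higher dose. The SAP states no PASS range to reproduce.

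**Score (SAP 7.3.1).** PASS = 100 × organs + 25 × SIRS criteria + 5 × pain + 5 × MED + 40 × (no solid diet), where 1 MED = 1 mg parenteral morphine.

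Maximum of the four bounded items: 3 × 100 + 4 × 25 + 10 × 5 + 40 = 300 + 100 + 50 + 40 = 490.

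**IV morphine equivalent that matches each item (points ÷ 5):**

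| Item | Points | mg |
|---|---|---|
| One SIRS criterion | 25 | 5 |
| Solid diet not tolerated | 40 | 8 |
| Maximum pain | 50 | 10 |
| One failed organ | 100 | 20 |
| Three failed organs | 300 | 60 |
| All other items at maximum | 490 | 98 |

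By the SAP's conversion table, 20 mg IV morphine is 20 × 1.5/10 = 3 mg IV hydromorphone, or 20 × 0.1/10 = 0.2 mg IV fentanyl.

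**Effect on ranking (constructed patients).**
- A: no organ failure, one SIRS criterion, pain 3, no solid diet, 40 MED. 0 + 25 + 15 + 200 + 40 = 280.
- B: one organ failure, three SIRS criteria, pain 5, no solid diet, 4 MED. 100 + 75 + 25 + 20 + 40 = 260.

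Without the opioid item A scores 80 and B scores 240, so the order reverses.

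**Effect on group means.** A difference of 5 mg per window between groups shifts mean PASS by 25 points, and a difference of 20 mg by 100.

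For a single patient, assume opioid dose accrues over 12 hours (the SAP's scoring interval; it names no separate opioid window) and IV fentanyl runs at 25, 50 or 100 micrograms/h. These rates are assumptions and are not in the documents.

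MED = rate × 12 / 1000 / 0.1 × 10; points = 5 × MED; mean shift = points / n.

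| Rate (micrograms/h) | MED | Points | Shift, n = 6 | Shift, n = 12 |
|---|---|---|---|---|
| 25 | 30 | 150 | 25 | 12.5 |
| 50 | 60 | 300 | 50 | 25 |
| 100 | 120 | 600 | 100 | 50 |

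**The conflicting unit.** If 1 MED meant 30 mg oral morphine, which is 10 mg IV by the same table, the weight would be 5/10 = 0.5 points per IV mg. One failed organ would then need 200 mg, and every opioid figure above would be ten times smaller.

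**Can the opioid share be recovered from other outputs?** Compare the PASS items with the related endpoints:
- Pain: PASS takes the highest rating in each 12-hour window; SAP 7.11 uses a daily mean.
- SIRS: the PASS version omits PaCO2 and band forms, which SAP 7.6 includes.
- Organ failure: PASS uses the Modified Marshall score; SAP 7.7 uses another definition and gives listings only.
- Diet: prospective PASS scoring also requires no vomiting or increase in pain; SAP 7.4 requires only that at least 50% is tolerated.
- Opioids: no summary of morphine-equivalent dose exists.

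The related endpoints do not add up to PASS, so the opioid part cannot be obtained by subtraction from the planned tables.

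**The case against.** Several points on the other side stand.

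- **Extreme patients are not hidden in the tables.** SAP 4.5 defines summary statistics to include the median, minimum and maximum, and adds patient listings. One outlying patient would show there. The mean graph gives no such protection.
- **The other four items have related measures elsewhere.** A PASS difference absent from all of them would point towards opioids. A reader might infer that a PASS difference can never be attributed; that is too strong. The pointer is indirect, however, because the definitions and windows differ.
- **Medication data are listed and tabulated by ATC code.** This shows which drugs were used, not dose in morphine equivalents by group and visit. The general rule in SAP 4.5 covers data collected, whereas MED is derived, so it does not clearly fill the gap.
- **The size is hypothetical.** The documents give no expected opioid doses. A reader might infer that opioids will decide the PASS curves, or that they disadvantage the controls. Neither is supported: the direction is unknown, and because SAP 4.5 splits tables by dose group, the lower-dose mean is as sensitive as the control mean.
- **Sedation.** A reader might infer that a sedation infusion is scored as disease activity. SAP 7.3.1 does not say whether opioid given for sedation counts, non-opioid sedatives would add nothing, and a ventilated patient already scores 100 for respiratory failure.
- **An opioid-free PASS has its own bias.** Analgesia lowers reported pain, so removing the opioid item flatters heavily treated patients. It cannot be the sole test of whether a PASS difference is real.
- **PASS is one of many untested secondary endpoints**, the primary endpoint is safety, and the opioid weight is part of the score as defined. This limits the consequence but does not remove the gap.

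**Conclusion.** The point holds as a reporting gap. PASS contains an uncapped item that depends on open-label prescribing, and the plan shows neither that item nor PASS without it. A between-group difference in PASS could therefore reflect prescribing rather than disease activity, and the planned tables would not show which.

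The equivalences (20 mg for one failed organ, 98 mg for the 490-point maximum) follow from the SAP's weights and rest only on the line that defines 1 MED as 1 mg parenteral morphine. The shifts of 25 to 100 points for a 6-patient group and 12.5 to 50 for the 12-patient group also assume a 12-hour window, the stated fentanyl rates, and that the fentanyl counts towards MED. Distortion is possible, not established.

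The two MED lines in SAP 7.3.1 contradict each other by a factor of ten. That matters in itself, because an error of that size in programming would be hard to see in a total.

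**What to change.** In SAP 7.3.3, keep the PASS total and its graph, and add:

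1. summary statistics by treatment and dose group and by visit for each of the five PASS components, including morphine-equivalent dose, as SAP 7.8.3 does for SOFA and 7.2.3 for the CT scales;
2. a supportive PASS without the opioid item, read alongside the total and the pain item because analgesia lowers reported pain.

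In SAP 7.3.1, reconcile the two MED definitions before the derivation is programmed. The hydromorphone conversions belong in the same check: the IV-to-oral ratio is written as 1 to 4 but its example of 1.5 to 7.5 mg is 1 to 5, and IV hydromorphone to IV morphine is written as 1 to 7 but the table gives 10/1.5 = 6.67.

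No formal rule for when PASS may be read as disease activity is needed. Nor is a flag for sedation use, which would require an indication that Protocol 8.11.2 does not list among the recorded items. Medians are already planned for the tables.

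**Cost:** SAP wording and a few more tables. Protocol 8.11.2 already records analgesic doses with times and routes, so no new data are required. The downside is that the headline PASS curve may look less favourable beside its components.

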7.4 Secondary Endpoints – Solid food

7.4.1 Definition

The definition of tolerating solid food is that at least 50% is tolerated. Then will the time to first occurrence of tolerating solid food be calculated as date of tolerating solid food – date of randomization +1.

At each visit will tolerating solid food be coded into yes or no.

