### 8.11.5 Vital Signs

The recorded vital signs must include the patient’s current temperature, heart rate (beats per minute), systolic and diastolic blood pressures, respiratory rate (breaths per minute), and the total input and output of fluids. The highest and lowest temperatures, the highest heart rate, and the highest respiratory rate since the prior study-required assessment will also be recorded. The total input of fluids (oral and intravenous) and the total output of fluids (urine output and nasogastric output) since the prior study-required assessment will be recorded.

If the patient has been started on vasopressor therapy since the prior study-required assessment, the start time should be recorded. If the patient has been placed on renal replacement therapy since the prior study-required assessment, the type of therapy will be recorded. If the patient has been placed on mechanical ventilation since the prior study-required assessment, the type of ventilation will be recorded (noninvasive or invasive mechanical ventilation). The current settings for fraction of inspired oxygen (FiO2), respiratory rate, tidal volume and positive end-expiratory pressure (PEEP) at the assessment will be recorded. If intra-abdominal pressures are being monitored, the current pressure and the highest pressure since the prior study-required assessment should be recorded. All solid food intake since the prior study-required assessment will be recorded including the time and date of the meal, the percent of the meal completed, if there were nausea or vomiting with the meal, and if pain medications had to be given one hour prior to or after the meal to treat symptoms due to ingesting the meal.

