7.4.3 Presentation

The variable tolerating food as yes/no will be presented using frequency tables.

The variable tolerating food as percentage will be presented using summary statistics.

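### SAP 7.4.1 defines tolerating solid food by a 50% threshold alone, while the PASS diet item in SAP 7.3.1 also requires no vomiting and no increase in abdominal pain

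*SAP*

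**What the plan says.** SAP 3.1.4 lists the PASS score and tolerating solid food as separate secondary efficacy endpoints.

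- **Solid-food endpoint.** SAP 7.4.1: "The definition of tolerating solid food is that at least 50% is tolerated". Two variables follow from it. One is a time: "Then will the time to first occurrence of tolerating solid food be calculated as date of tolerating solid food – date of randomization +1". The other is a code by visit: "At each visit will tolerating solid food be coded into yes or no". SAP 7.4.3 adds: "The variable tolerating food as percentage will be presented using summary statistics".
- **PASS diet item.** SAP 7.3.1 weights it as "Tolerating Solid Diet Score: (yes=0, no=1) x 40" and gives two ways to decide yes or no: "Retrospective analysis: based on change in diet order" and "Prospective analysis: tolerating at least 50% of solid meal without increase abdominal pain or vomiting". It does not say which one this trial uses.
- **Data collected.** Protocol 8.11.5 records, for solid food since the previous assessment, when the meal was taken, the percent completed, "if there were nausea or vomiting with the meal", and whether pain medication was needed within an hour before or after it for symptoms caused by eating.

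The efficacy lists in protocol 10.2 and 10.4 name neither PASS nor solid food, and protocol 10.4 makes the SAP decisive for all analyses. The definition can therefore only be settled in the SAP.

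**The concern.** The same clinical idea is measured twice in one SAP, with symptom conditions in one place and none in the other. Someone programming 7.4.1 as written would use the percent-completed field alone. A half-eaten meal followed by vomiting would then count as the first success in the food endpoint and as a failure in PASS.

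At stake are the yes/no frequencies and the time to tolerance in a listed efficacy endpoint. The trial is open-label, so a definition left to be settled during programming could be questioned later as chosen with treatment and outcomes in view.

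**Working it through.** The plan states no figure to reproduce here. The check compares the definitions and then does simple arithmetic on the planned group sizes.

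**1. One meal under each rule**

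| Meal | SAP 7.4.1, read literally | PASS prospective rule, SAP 7.3.1 |
|---|---|---|
| Under 50% eaten | no | no |
| At least 50%, no symptoms | yes | yes |
| At least 50%, then vomiting | yes | no |
| At least 50%, abdominal pain increased | yes | no |

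The rules part only in the last two rows, and always in the same direction.

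**2. Is the literal reading of 7.4.1 the likelier one?** The sentence is circular: tolerating means that 50% is tolerated. Three features point to a plain percentage. The PASS rule adds its symptom condition on top of tolerating at least 50%, so there the threshold does not already contain the condition. SAP 7.4.3 summarises tolerance as a percentage. The only meal percentage listed in protocol 8.11.5 is the percent completed, recorded apart from symptoms.

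**3. Effect on time to tolerance.** Let r be the randomization date, a the date of the first meal at least 50% eaten, and b the date of the first such meal without vomiting or increased pain. Every meal that meets the stricter rule meets the looser one, so b ≥ a.

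- Looser time: a − r + 1
- Stricter time: b − r + 1
- Difference: b − a ≥ 0

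The difference is zero if a symptom-free meal follows on the same date, and at least one day otherwise. The documents give no rate of failed meals and no interval between meals, so nothing more can be said about its size.

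**4. Effect on the tolerating percentage.** Cohorts of 4, 4, 8 and 8 (SAP 3.2) total 24, as in SAP 3.3. Randomization at 3:1 gives 3, 3, 6 and 6 on active treatment and 1, 1, 2 and 2 on supportive care.

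- First-phase dose: 3 + 3 = 6; one patient = 100/6 = 16.7 percentage points
- Second-phase dose: 6 + 6 = 12; one patient = 100/12 = 8.3 percentage points
- Supportive care: 1 + 1 + 2 + 2 = 6; one patient = 100/6 = 16.7 percentage points

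These figures assume that every planned patient is assessed at the visit. After discharges the denominators shrink and one patient weighs more.

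**5. Effect on PASS.** None. The diet item is scored by the rule in 7.3.1 and takes no input from 7.4.1.

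**The case against.** The strongest reply is that 7.4.1 speaks of food tolerated, not food eaten. A vomited meal is not plainly tolerated, and 7.4.1 directly follows the PASS section with the same threshold, so it may be shorthand for the PASS rule. This stands in part: the SAP nowhere states that a vomited meal counts as a success. But on that reading the rule still cannot be derived from the recorded items without saying which symptoms disqualify a meal, so the wording needs completing either way.

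It can also be said that the labels retrospective and prospective choose the PASS rule by themselves in a prospective trial. That is reasonable, and it leaves only a sentence of clarification to ask for. The retrospective line causes no miscalculation.

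A third reply is that little depends on this. SAP 7.3.2 and 7.4.2 plan no analyses, SAP 4.2 says the study is not powered for inference, and any looseness applies in every arm. All of that is correct and limits the weight of the point.

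Three stronger readings are tempting, and the documents do not support them:

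- **Each disagreement shifts PASS by 40 points.** Forty is the weight of the diet item. It would move only if PASS adopted the looser rule.
- **Time to food typically shifts by a day or more.** Neither document has a source for this, and a shift of zero is possible because dates are used.
- **Two endpoints share one name and disagree.** The overlap is between the food endpoint and one component of PASS, not between two endpoints of the same name.

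**Conclusion.** The point holds as an inconsistency of definition. SAP 7.4.1 lacks the symptom conditions that SAP 7.3.1 applies to the same idea, and nothing in either document reconciles them. On the literal reading, the food endpoint can only look the same or more favourable than under the PASS rule: times no later, yes-rates no lower. One discordant patient is worth 16.7 or 8.3 percentage points in a planned group; the number of such patients is unknown.

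The conclusion rests on reading 7.4.1 as a percentage rule, which the SAP's own usage favours but does not state, and on the prospective rule being the one used for PASS. No difference between arms is shown. The primary safety endpoints, the sample size and error rates are untouched. It should be corrected before database lock, but it does not threaten the trial's main conclusions.

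**What to change.** - **SAP 7.4.1:** replace the definition by a cross-reference to the PASS prospective rule in 7.3.1: at least half of a solid meal, with neither vomiting nor increased abdominal pain. Use it for both the visit code and the time variable.
- **SAP 7.3.1:** state that the prospective rule applies in this trial.
- **Derivation:** build one yes/no item from the meal data of protocol 8.11.5 and use it for both endpoints. Protocol 8.11.5 mentions nausea and vomiting together, so say how vomiting is identified. It lists no meal-linked pain rating. If pain medication within one hour of the meal stands in for increased pain, call it a proxy and apply it identically in both sections; putting it in 7.4.1 alone would leave two pain rules.
- **Alternative:** if the two definitions are meant to differ, say so and name the food variable for what it measures, such as first meal at least half eaten.

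The cost is SAP wording and one shared derivation, with no new data collection. Times to tolerance become equal or slightly longer. A patient with no symptom-free meal on record would have no time, a case 7.4.1 already leaves open for patients who never reach 50%.

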7.4.2 Analysis

No analyses will be performed

7.4.3 Presentation

The variable tolerating food as yes/no will be presented using frequency tables.

The variable tolerating food as percentage will be presented using summary statistics.

